Common adverse events	
 
- mild to moderate adverse gastrointestinal side effects
 
- In the largest (n = 119), longest (52 weeks), and highest-dose (ending with 2 g by mouth daily) human study of resveratrol to date, a total of 104 participants completed the phase II study. Inclusion criteria individuals >49 years old with a diagnosis of mild-to-moderate dementia due to AD, with stable medications and medically stable. No differences were found between the resveratrol and placebo-treated groups in terms of safety and tolerability, with the only exception being weight loss in the resveratrol-treated group. The most common reported AEs were nausea and diarrhea, with 42% reported in the resveratrol group versus 33% in the placebo group. The difference between groups was not statistically significant different. The high background of gastrointestinal AEs is likely due to concomitant treatment with a cholinesterase
 
	12,10,11,14

	inhibitor approved for Alzheimer disease. Weight loss in the resveratrol-treated group may be due to enhanced mitochondrial biogenesis mediated by SIRT1.	
Serious adverse events	- Renal failure with SRT501 (a micronized oral formulation of resveratrol) and bortezomid  - fever and bicytopenia 	12,14
Expected adverse events	- nausea and diarrhea	12,10,11,14
No adverse events discussed		15-31

Most studies did not show or discuss adverse events. Our study dosage at 125 mg/day for adults are far below these levels of 0.5 to 5 g per day which were associated with gastrointestinal distress.

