## 4 STUDY DESIGN AND ENDPOINTS

### 4.1 DESCRIPTION OF THE STUDY DESIGN

The study has a 2x2 crossover design. Participants will take either the placebo or resveratrol for 90 days followed by a 30 day washout period and the placebo or resveratrol for the last 90 days. 30 day washout period was chosen in order to eliminate any carry over from resveratrol as it is recommended to avoid resveratrol 2 weeks prior to surgery suggesting that carry over could potentially be as long as 2 weeks (<http://www.webmd.com/vitamins-supplements/ingredientmono-307-resveratrol.aspx?activeingredientid=307>; <http://ww5.komen.org/BreastCancer/Resveratrol.html>). Participants will be mailed a 30 or 90 day (for international participants) supply of placebo or resveratrol which they will receive 5 days before the end of each 30 day period (not applicable for international participants). Participants will keep daily pain log of pain and activity levels during the entire 210 day study period. We recognize that this is a long period of time however this population is highly motivated because 1) their pain is not systematically treated, 2) currently available over the counter NSAIDs, frequently used to control pain, cause gastrointestinal issues when used for prolonged periods and 3) participants reached through Little People of America and the PSACH facebook page are actively seeking solutions to control pain. This is being co-ordinated by a single center and will enroll 30 PSACH individuals. Because this is a rare condition, participants from 18 years - to 70 years will be enrolled.

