#### **Follow-up Visit (Visit 4, Day 90 +/- 5 working days)**

- Inform patient that they are supposed to not take any study medication for the next 30 days but should continue their pain logs.
- Record adverse events as reported by participant to study co-ordinator. Study coordinator will ask about gastrointestinal health, any bleeding events and unusual bruising. PI will follow up with participant to assess the adverse events and determine whether to terminate participation.
- Record participant's adherence to treatment protocol.
- Inquire about any medication and health condition changes.
- Administer HRQoL instrument.
- Request participant to mail back or email their pain log and mail back any unused medication or email a photo of the empty bottle. The data from the pain logs will be compiled and analyzed at the start and end of each two treatment periods (on days 0, 90, 120, and 210).
- Ask participants about which medication, resveratrol or placebo, they think they were taking during the last 90 day period (evaluation of the success of blinding).
- Female participants in the United States will be asked to take a urine pregnancy test at local labcorp or local lab. Email a photo of self administered pregnancy test supplied by us for female international participants within 30 days prior to next medication mail out.
- Participants will be asked to complete blood draw to the closest LabCorp or from their local facility at our cost. For the International participants complete blood draw to the closest local facility blood and mailed to us for analysis at local Labcorp lab.
- The complete metabolic panel includes analysis of renal function [blood urea nitrogen (BUN), creatinine], liver function [total bilirubin, alanine aminotransferase (ALT), alkaline phosphatase (ALP), and aspartate aminotransferase (AST)], glucose, electrolytes [calcium, sodium, potassium, carbon dioxide (bicarbonate), chloride], protein [albumin, total protein]. The complete blood count (CBC) includes analysis of red blood count, hemoglobin, hematocrit, white blood cell count, platelet count. Platelet count below 50,000 per  $\mu$ l in CBC which indicates increased bleeding risk will result in removal from the study.

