## 10.3 ANALYSIS DATASETS

The dataset analyzed will be comprise of demographic and clinical information obtained from the patient, the pain scores obtained from the pain and HRQoL instruments described above. The database will be maintained by the study coordinator and will be password-protected and stored on the secure and HIPAA-compliant University of Texas Health Science Center's zone 100 network. It will be accessible only to the study staff.

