#### 10.4.4 SAFETY ANALYSES

The study DSMB will meet after every 10 patients have successfully completed the full study and all study data has been completed. The DSMB will be presented with all study-duration events (signs/symptoms/co-morbidities) that have been ascertained from all the patients that have completed their participation in the study and will be classified as study-related vs. incidental. The crude rate of the study-related event(s) will be tabulated with one-sided 95% confidence intervals. Additionally, for study-related events that occur in more than 5 patients will be further analyzed to incorporate duration of exposure to study drug.

---

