### 10.5 SAMPLE SIZE

Although studies haven't quantified pain variability in PSACH, other studies have utilized a pain VAS and have reported standard deviation (SD) of the difference between scores for the same patient of about 10-15 on a 1-100 scale. In addition, previous research by one of the investigators has suggested that a strong placebo effect can be present in studies using the pain VAS at a magnitude of about 20 on a 1-100 scale. Assuming a similar degree of variability in our study population and considering the placebo effect as reported, with a sample size of 30 participants at a Type I error rate of 5%, the minimal detectable difference would be 2.8 units at a SD of 10 and power of 80%, 4.25 at a SD of 15 and power of 80%, 3.3 at a SD of 10 and power of 90%, and 4.9 at a SD of 15 and power of 90%. Considering that there are about 300 potential patients that can be approached through the "Little People of America" support group and the Facebook PSACH group, we should be able to recruit into the study at least half of those highly motivated and invested individuals. We should be able to achieve our sample size of 30 patients for this study, even assuming a considerably high 33% attrition rate. We will screen 60 to enroll 30.

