#### 10.6.1 ENROLLMENT/ RANDOMIZATION/ MASKING PROCEDURES

One hundred individuals with PSACH will be enrolled in the study and then randomized to receiving resveratrol or placebo first based on randomization assignment by biostatistician. We will not replace enrollees that drop out as we have statistical power to lose 10% of the cohort and still determine whether the supplement provides relief of pain. All study participants will be blinded to the study drug. All study investigators and analysts will be blinded to the study drug with the exception of the study coordinator who will be responsible for mailing out the study medications.

---

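### Blood panels are drawn at baseline, around Day 90 and at Day 210, but no analysis compares the laboratory values between resveratrol and placebo

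*Combined protocol and SAP*

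**What the plan says.** Section 4.1 sets the frame: "The study has a 2x2 crossover design", so every participant who completes takes both products.

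Blood is collected three times. Section 7.3.2 describes a metabolic panel and blood count at baseline. The Visit 4 text in 7.3.3 (Day 90) repeats both: "Participants will be asked to complete blood draw to the closest LabCorp or from their local facility at our cost". Section 7.3.4 repeats them at Day 210. The schedule table in 7.3.7 marks the second blood test in the washout column rather than under Visit 4. No draw is planned at Day 120.

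In the analysis sections, 10.3 lists demographic and clinical information and "the pain scores obtained from the pain and HRQoL instruments described above". The models in 10.4.1 to 10.4.3 concern pain and quality of life. Section 10.4.4 deals with signs, symptoms and co-morbidities: "The crude rate of the study-related event(s) will be tabulated with one-sided 95% confidence intervals". Study-related events seen in more than 5 patients are analysed further for duration of exposure. No split by product received is specified.

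Laboratory results are used elsewhere as thresholds: the platelet rule (5.2, 7.3.2 to 7.3.4), CTCAE grading of creatinine, potassium, ALT, ALP, AST, bilirubin, platelets and haemoglobin (8.2.1), and the halting rules, one of which is specific to liver function (8.5).

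**The concern.** The trial pays for numeric laboratory data in a design where each participant can be their own control, and then plans no summary, change from baseline, shift table or product comparison of those values. For most of the graded parameters, grade 1 begins at the edge of the normal range. A consistent movement in liver enzymes, creatinine, platelets or haemoglobin that stays inside that range would enter no planned analysis.

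Counts of events in about 30 people say little about a product. A report resting on them alone could find nothing notable while values already on file, never compared, pointed to a shift.

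**Working it through.** **The plan's own figure.** The documents give no figure for any laboratory comparison. Their only calculation, in 10.5, is for pain. It uses a "standard deviation (SD) of the difference between scores for the same patient of about 10-15 on a 1-100 scale" and states a detectable difference of 2.8 units with 30 participants, SD 10 and 80% power. The paired formula is (1.960 + 0.842) × SD / √n.
- n = 30: 2.802 × 10 / 5.477 = 5.11 (about 5.3 with the t distribution).
- n = 100: 2.802 × 10 / 10 = 2.80.

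So 2.8 does not reproduce at 30. It matches the figure in 10.6.1: "One hundred individuals with PSACH will be enrolled in the study". That is a separate problem, but it is why several values of n are shown below.

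**Inputs.** n = 30 (4.1, 10.5); n = 27 after the 10% loss in 10.6.1; n = 20 after the 33% attrition in 10.5 (30 × 0.67 ≈ 20); n = 100 (10.6.1). Laboratory SD: not given, so results are in units of the SD of the within-participant difference.

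**What event counts can exclude.** With zero events, the one-sided 95% upper bound is 1 − 0.05^(1/n).

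**What a paired contrast can detect.** The period-adjusted estimate is half the difference between the two sequences in mean (period 1 − period 2). With equal sequences its standard error is SD_diff/√n, on n − 2 degrees of freedom. The detectable shift d (80% power, two-sided 5%) solves P[T′(n − 2, d√n) > t(0.975, n − 2)] = 0.80, where T′ is noncentral t.

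| n | Upper bound, zero events | Detectable shift (SD of difference) |
|---|---|---|
| 20 | 13.9% | 0.66 |
| 27 | 10.5% | 0.56 |
| 30 | 9.5% | 0.53 |
| 100 | 3.0% | 0.28 |

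The two columns measure different things and cannot be ranked against each other. They show only what each analysis can resolve.

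**Illustration on assumptions that are not in the documents.** Put the upper limit of normal 1.96 between-patient SDs above the mean and take a within-patient correlation of 0.5 to 0.7, with n = 30 (20,000 simulated trials). The table compares a paired t-test on the values with an exact McNemar test on values above the limit.

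| True shift (between-patient SD) | Power, paired test | Power, threshold test |
|---|---|---|
| 0.3 | 36–54% | about 0.1% |
| 0.5 | 75–93% | 0.5–0.7% |
| 0.7 | 96–99.8% | 3–4% |

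**Why the draw date matters.** A draw in washout may be up to 30 days off product. Suppose a shift δ had fully reversed by then. In the resveratrol-first sequence, period 1 − period 2 would have mean π (the period effect); in the placebo-first sequence, π − δ. Half the difference is ½[π − (π − δ)] = δ/2. In that extreme case the contrast keeps half the effect.

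**The case against.** **Laboratory data are not ignored.** They enter through CTCAE grades, the platelet rule and the halting rules. On the illustrative assumptions above, the chance that at least three of 30 values exceed the upper limit at one draw rises from about 4% with no shift (2.5% per value) to about 37% with a 0.5 SD shift (7.2% per value). The liver-function halting rule therefore has some sensitivity to drift, and the McNemar test is not a rule in the plan. This stands. But that trigger counts values whichever product was taken, so it does not compare resveratrol with placebo.

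**A reader might infer that events will be pooled across products.** The text does not say so. Section 8.6 has the DSMB assess each arm, and 10.4.7.1 gives it unblinded information. What can be said is that 10.4.4 specifies no split by product received. The word arm does not settle it: the schedule table uses it for a treatment period, 6.2 and 10.6.3 for the randomised assignment.

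**Clinical information in 10.3 could be read to include laboratory results, and the DSMB charter may ask for them.** Both are possible, but neither is a stated analysis. The reference cited in 10.4.4 is titled as being about laboratory data, which does not make it one.

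**The paired contrast has limits.** Different laboratories may serve the same participant and inflate the SD. Seven analytes at 5% give 1 − 0.95^7 ≈ 30% chance of at least one false signal if independent. Both points stand and are reasons to label the intervals descriptive.

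**Body weight is a separate matter.** Section 2.3.1 reports no safety difference from placebo in its longest cited trial, "with the only exception being weight loss in the resveratrol-treated group", and no visit records weight. That trial reached 2 g/day in patients with dementia, 16 times the 125 mg/day here (2000/125). Whether to collect weight is a data-collection choice and forms no part of this point.

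**Conclusion.** The point holds in a limited form. Laboratory values are collected three times, no section names an analysis of them, and 10.4.4 specifies no split by product. What is lost is the numeric comparison between products inside the grade and rule limits; graded abnormalities are still captured.

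At n = 30 the paired contrast would resolve about 0.53 SD of the within-participant difference (0.66 SD at 20), while zero events would exclude only rates above 9.5% (13.9% at 20). The 20-participant case is pessimistic, since 10.6.1 plans for a 10% loss. These figures assume roughly normal differences, equal sequences and on-product draws in both periods. The last depends on resolving the conflict between Visit 4 and the schedule table.

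A reader might go further and call this the trial's most sensitive safety comparison. The documents do not support that: they give no laboratory SD, and the adverse events they expect, nausea and diarrhoea, are not what these panels measure. The change should be made because the data are already being paid for. It does not affect the primary pain analysis.

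**What to change.** 1. Reconcile the Visit 4 text (draw at Day 90) with the schedule table in 7.3.7 (draw under washout). Bring 7.2.1 (marked not applicable) and 13.4.1 (no specimens collected) into line with the draws that are planned.
2. In 10.3, name laboratory results as part of the dataset, with the draw date and the date of last dose for each sample.
3. In 10.4.4, tabulate study-related events by product received, showing events in washout separately.
4. In 10.4.4, for ALT, AST, ALP, bilirubin, creatinine, platelets and haemoglobin, report the within-participant resveratrol-minus-placebo difference in end-of-period values, adjusted for period, with 95% confidence intervals labelled descriptive. No Day 120 draw is needed for this. Add a CTCAE grade-shift table by product.

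The cost is analysis-plan wording, three tables and two dates per sample, with no extra blood draws or recruitment. The downsides are several intervals without multiplicity adjustment and added variability where laboratories differ between draws.

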#### 10.4.5 ADHERENCE AND RETENTION ANALYSES

At the end of each intervention period, subjects will be asked to complete two questions on adherence. The first question will incorporate a visual analog scale (VAS) as a means to calculate self-reported adherence to study medication use. The second question will inquire about reasons for their non-compliance if any. These scales will be assessed after successful completion of every 10 patients so that any issues with adherence may be identified early and rectified for subsequent study participants.

---

#### 10.4.6 BASELINE DESCRIPTIVE STATISTICS

Baseline descriptive statistics will be presented for demographic and clinical information for each patient. These will be tabulated and described as frequencies and percentages (for categorical data) and mean and standard deviations or median and inter-quartile ranges (for normally distributed and non-normally distributed continuous data, respectively). No statistical comparisons will be performed between the two as this is a randomized clinical trial.

---

#### 10.4.7 PLANNED INTERIM ANALYSES

None

---

##### 10.4.7.1 SAFETY REVIEW

The study DSMB will meet after every 10 patients have successfully completed the full study and all study data has been completed. Nonblinded information on all study-duration events (signs/symptoms/co-morbidities) that have been ascertained from all the patients will be classified as study-related vs. incidental.

---

##### 10.4.7.2 EFFICACY REVIEW

There will be no interim analysis to assess efficacy performed for this study as this is a rare condition and there are a finite number of patients available for recruitment into the study. Adjusting the Type I error rate and recruiting additional patients is not achievable. However, safety assessments will be ongoing by the DSMB as described in section 8.6

---

#### 10.4.8 ADDITIONAL SUB-GROUP ANALYSES

None

---

#### 10.4.9 MULTIPLE COMPARISON/MULTIPLICITY

The design incorporates repeated measurements. The statistical models will account for that.

---

#### 10.4.10 TABULATION OF INDIVIDUAL RESPONSE DATA

Tabulation of individual response data for regulatory bodies will be provided as needed. The data included per patient will be dependent on the study report being presented. If needed all repeated measurements from every study subject will be presented in the appropriate tables.

---

#### 10.4.11 EXPLORATORY ANALYSES

None

### 10.5 SAMPLE SIZE

Although studies haven't quantified pain variability in PSACH, other studies have utilized a pain VAS and have reported standard deviation (SD) of the difference between scores for the same patient of about 10-15 on a 1-100 scale. In addition, previous research by one of the investigators has suggested that a strong placebo effect can be present in studies using the pain VAS at a magnitude of about 20 on a 1-100 scale. Assuming a similar degree of variability in our study population and considering the placebo effect as reported, with a sample size of 30 participants at a Type I error rate of 5%, the minimal detectable difference would be 2.8 units at a SD of 10 and power of 80%, 4.25 at a SD of 15 and power of 80%, 3.3 at a SD of 10 and power of 90%, and 4.9 at a SD of 15 and power of 90%. Considering that there are about 300 potential patients that can be approached through the "Little People of America" support group and the Facebook PSACH group, we should be able to recruit into the study at least half of those highly motivated and invested individuals. We should be able to achieve our sample size of 30 patients for this study, even assuming a considerably high 33% attrition rate. We will screen 60 to enroll 30.

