#### 10.6.2 EVALUATION OF SUCCESS OF BLINDING

At the end of each study period, all study subjects will be asked to respond to a single question asking them to identify if they were on the study drug or placebo during the previous intervention period. This data will be analyzed after 20, 40 and all subjects have completed the study to evaluate the success of blinding.

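### The four minimal detectable differences given for 30 participants do not follow from n = 30 (paired t-test values are about 1.9 times larger two-sided, 1.65 times one-sided), and enrolment is stated as both 30 and 100

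*Combined protocol and SAP*

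**What the plan says.** All inputs to the power statement are in section 10.5 (Sample Size). The SD is that "of the difference between scores for the same patient of about 10-15 on a 1-100 scale". The calculation is made "with a sample size of 30 participants at a Type I error rate of 5" percent. From these, "the minimal detectable difference would be 2.8 units at a SD of 10 and power of 80%, 4.25 at a SD of 15" at 80% power, with 3.3 (SD 10) and 4.9 (SD 15) at 90% power. The section does not say whether the test is one- or two-sided and names no formula. It says that a placebo effect was considered but not how.

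The number of participants appears in three places:

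- Section 4.1 (Description of the Study Design): the single centre "will enroll 30 PSACH individuals".
- Section 10.5: "We will screen 60 to enroll 30".
- Section 10.6.1 (Enrollment/Randomization/Masking Procedures): "One hundred individuals with PSACH will be enrolled in the study".

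Two further statements depend on that number. Section 10.6.1 says "We will not replace enrollees that drop out as we have statistical power to lose 10% of the cohort", and section 10.6.2 says of the blinding question that "This data will be analyzed after 20, 40 and all subjects have completed the study".

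**The concern.** A 2x2 crossover with a known SD of the within-patient difference has a simple detectable-difference formula, so the four figures can be checked directly. With 30 patients and an SD of 10, the standard error of the mean difference is 10/√30 = 1.83. A stated difference of 2.8 is only about 1.5 standard errors, whereas 80% power at two-sided 5% needs about 2.8 standard errors.

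These are the only power figures in the protocol. If they are wrong, it overstates what 30 participants can detect, and the decision not to replace dropouts rests on a power claim with no sound figure behind it. The conflict between 30 and 100 also leaves an ethics committee, the DSMB or any other reader unsure how many people will be randomised.

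**Working it through.** **Inputs.** n = 30, type I error 5%, SD of the within-patient difference 10 or 15 on a 1-100 scale, and power 80% or 90% (all section 10.5); 2x2 crossover (section 4.1). Both sidedness cases are run because section 10.5 does not state one and the hypothesis in section 10.2 is directional.

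**Formula.** Normal approximation: MDD = SD × (z for alpha + z for power) / √n. The exact version finds the difference at which a paired t-test with n − 1 degrees of freedom reaches the required power, using the noncentral t distribution.

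**Step 1: try to reproduce the plan's figures at n = 30.** For SD 10, 80% power, two-sided, the normal approximation is 10 × (1.960 + 0.842) / 5.477 = 5.12, against the stated 2.8. All four cases:

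| | SD 10, 80% | SD 15, 80% | SD 10, 90% | SD 15, 90% |
|---|---|---|---|---|
| Stated in 10.5 | 2.8 | 4.25 | 3.3 | 4.9 |
| n = 30, two-sided, normal | 5.12 | 7.67 | 5.92 | 8.88 |
| n = 30, two-sided, exact t | 5.29 | 7.94 | 6.12 | 9.19 |
| Ratio to stated (two-sided t) | 1.89 | 1.87 | 1.86 | 1.87 |
| n = 30, one-sided, exact t | 4.65 | 6.97 | 5.47 | 8.21 |
| Ratio to stated (one-sided t) | 1.66 | 1.64 | 1.66 | 1.68 |

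Using n − 2 degrees of freedom, as for a sequence-adjusted crossover, changes the two-sided values only to 5.30, 7.95, 6.13 and 9.20.

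**Step 2: power at n = 30 for the stated differences.**

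| | SD 10, d = 2.8 | SD 15, d = 4.25 | SD 10, d = 3.3 | SD 15, d = 4.9 |
|---|---|---|---|---|
| Claimed | 80% | 80% | 90% | 90% |
| Two-sided | 32% | 32% | 42% | 41% |
| One-sided | 44% | 45% | 55% | 54% |

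**Step 3: what would produce the stated figures.**

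- Two-sided, the smallest n reaching the claimed power is 103, 100, 99 and 101. At n = 100 the exact values are 2.83, 4.24, 3.27 and 4.91, a match to within about 1%.
- One-sided, the required n is 81, 79, 81 and 82. No section mentions a number near 80.
- With n held at 30, the SDs would have to be about 5.3 and 8.0 two-sided, or about 6.0 and 9.0 one-sided, not 10 and 15.
- If 10 to 15 were instead the within-patient SD of a single score, the SD of the difference would be √2 times larger. The two-sided values at n = 30 would then be about 7.5, 11.2, 8.7 and 13.0, further from those stated.
- Parallel arms of 15 or 30, halved differences, and 60 or 90 effective observations also fail to give the four figures.

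**Step 4: enrolment and attrition.** Sections 4.1 and 10.5 say 30; section 10.6.1 says one hundred. A blinding look after 40 completers (section 10.6.2) cannot occur with 30 enrolled. Section 10.5 speaks of 33% attrition and section 10.6.1 of a 10% loss, and the stated figures show no allowance for either. The effect on a cohort of 30 is:

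| Completers | Sides | SD 10, 80% | SD 15, 80% | SD 10, 90% | SD 15, 90% |
|---|---|---|---|---|---|
| 27 (10% lost) | Two | 5.60 | 8.40 | 6.48 | 9.72 |
| 27 (10% lost) | One | 4.92 | 7.37 | 5.79 | 8.68 |
| 20 (33% lost) | Two | 6.60 | 9.91 | 7.65 | 11.47 |

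**Step 5: scale.** The figures are on a 1-100 scale, whereas the trial scores pain from 0 to 10. Dividing by 10 is an assumption, since section 10.5 says pain variability in PSACH has not been quantified. On that basis the two-sided values at n = 30 are 0.53, 0.79, 0.61 and 0.92 points.

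**The case against.** **The practical effect is small.** Under the rescaling in step 5, every corrected value lies well below the 2-unit change in section 10.1 and the 2.8-point hypothesis in section 10.2. Two-sided power for 2 points stays above 99.9% even with SD 1.5 and 20 completers. The 32% to 42% powers concern differences of 2.8 to 4.9 on a 100-point scale, which no section calls clinically important. This stands, on the rescaling assumption, and it limits the weight of the point.

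**The planned analysis is richer than a paired t-test.** Section 10.4.1 specifies a multilevel mixed model with baseline and repeated measurements, and section 10.5 mentions the placebo effect. Either could in principle alter the precision. But section 10.5 gives no within-patient correlation, number of measurements or placebo adjustment, and it labels its SDs as 10 and 15. What stands is that the replacement figures must be labelled as paired t-test values at the stated SD.

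**The 30 may be the error, not the four figures.** If one hundred was intended, the figures are right to rounding. The recruitment text in section 10.5 could be read that way: half of about 300 is 150, and 33% attrition leaves about 100. That is an inference; no section says where the figures come from. Sections 4.1 and 10.5 both give 30, and section 10.5 attaches the figures to 30, so the text is wrong as written. The restatement should still follow whichever number is confirmed.

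**Conclusion.** The concern holds. At the sample size section 10.5 names, the four detectable differences are too small by a factor of 1.86 to 1.89 two-sided, or 1.64 to 1.68 one-sided. This rests on a paired t-test with the stated SDs of the within-patient difference; no standard variant tried recovers the figures at n = 30. The contradiction between 30 and one hundred is separate, is not corrected elsewhere in the protocol, and carries through to the blinding looks and the dropout statement.

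The error does not by itself show that 30 participants are too few. It should be fixed because the protocol's only power figures, and the number to be randomised, cannot be relied on as written.

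**What to change.** 1. Settle the enrolment number and state it identically in sections 4.1, 10.5 and 10.6.1.
2. In section 10.5, restate the four values for that number, naming method, sidedness and scale. For n = 30 (paired t-test, SD of the within-patient difference, 1-100 scale) they are 5.3 (SD 10, 80%), 7.9 (SD 15, 80%), 6.1 (SD 10, 90%) and 9.2 (SD 15, 90%) two-sided, or 4.6, 7.0, 5.5 and 8.2 one-sided. If 100 is confirmed, the present figures can stay as two-sided values, but the 30 beside them must change.
3. Express the detectable difference on the 0-10 scale used in sections 10.1 and 10.2, with the SD assumption stated.
4. Reconcile the 33% and 10% attrition figures, and tie the claim about losing 10% of the cohort to a named target difference and number of completers.
5. Reset the section 10.6.2 blinding looks to fit the enrolment.

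The cost is protocol wording only. If 30 is kept, the stated detectable differences become less favourable; nothing in the conduct of the trial changes apart from the timing of the blinding looks.
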